# FLOW CHART

Trial Periods	Screening 		Randomise	d Treatment					Follow-Up
Visit	1a 	1b 	2 	3	4	5	6	EoT / ED 	EoS 
Week	-4		R	1	2	4	6	8	10
Day	-28		1	8	15	29	43	57	71
Time window for visits (days)	See footnot	te 1	N/A	$+_{2}$	+ 2	$+_{2}$	± 3	± 5	± 5
Fasting status 	NF	F	F	NF	NF	F	NF	F	F
Informed consent	х								
Register patient in IRT system via IRT call	Х								
Demographics 	х								
Medical history / baseline conditions 	х								
Concomitant therapy	х	Х	х	х	х	х	х	х	х
Anthropometric measures 	х		х	х	х	х	х	х	х
Vital signs 	х		x 	x 	x 	x 	х	х	x
Physical examination 	x 		(x)	(x)	(x)	(x)	(x)	х	(x)
Resting 12-lead ECG 	х		x 	x 	x 	x 	х	х	х
Safety laboratory sampling	х		х	х	х	х		х	х
Pregnancy testing 	Xs		Xu			Xu		Xu	Xu
Hepatic venous pressure gradient (HVPG) 		х						х	
Ultrasound (liver and spleen) 		Х				х		х	х
Review of in-/exclusion criteria	x	x	x						
Randomisation			x						

BI-VQD-12177\_40-106\_AD-03 (22.0)

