- 9. Pregnancy testing required in women of child-bearing potential (WOCBP) only.  $x_s$  = serum testing;  $x_u$  = urine testing. Serum pregnancy will be done at screening (Visit 1a) and as a reflex when urine testing is positive. More frequent pregnancy testing should be done if required by local regulation and /or authority or per investigator judgement. Pregnancy testing at dosing visits should be completed prior to administration of trial medication. Refer to Section 5.2.3
- 10. For further details regarding the HVPG measurement, refer to Section 5.1.1
- 11. For further details regarding ultrasound of the liver and spleen, refer to Section 5.2.5.1
- 14. Electronic home BP monitoring equipment will be provided for a patient to measure BP and HR on a daily basis from Visit 2 (refer to Section 5.2.2.1). Following training on the use of the equipment at Visit 2, subsequent refresher training should be provided if required

17.

- 18. Biobanking sampling requires a consistent status from one sample to another in terms of fasting vs non-fasting; a fasting status is therefore defined. Sampling is optional and requires separate informed consent. Refer to Section 5.5
- 19. After the EoS visit (= individual trial participants end of the trial) the Investigator should report only the following: any cancers of new histology and exacerbations of existing cancer, trial medication related Serious Adverse Events (SAEs) and trial medication related Adverse Events of Special Interest (AESIs) of which the Investigator may become aware of. These should be reported only via the BI SAE form (refer to Section 5.2.6.2.1)
- 20. The physical examination at Visit 1a should include an assessment of the clinical criteria for Child-Turcotte-Pugh classification (refer to Appendix 10.3)

Boehringer Ingelheim		29 Nov 2023		
BI Trial No.: 136	6-0055			
c42374778-02	Clinical Trial Protocol	Page 9 of 98		
Proprietary confidential information © 2023 Boehringer Ingelheim International GmbH or one or more of its affiliated companies				

- 21. During the dose-titration period (i.e. when up-titration is occurring), and at the subsequent visit, vital signs and 12-lead ECGs will also be repeated approximately 1 hour and 2 hours after intake of the trial medication. Measurement of vital signs should precede the 12-lead ECG, and measurement of the 12-lead ECG should precede the 1 hour and (refer to Sections 5.2.2, 5.2.4 and 5.3).

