#### **1.2.3** Data from clinical studies

BI 685509 has been tested in a single rising dose trial, a food effect and DDI trial, two multiple rising dose (MRD) trials in male healthy volunteers, and one multiple oral rising dose trial in patients with DN. Overall, it was well tolerated except for dose limiting orthostatic dysregulation. In the single dose trials, BI 685509 appears to reduce diastolic and systolic BP with a compensatory increase in HR, however, up-titration and TID dosing markedly improved the cardiovascular tolerability of the drug.

Summary of data from Trial 1366-0020:

In the trial, 49 patients with hepatic impairment due to various underlying liver diseases were treated for up to 4 weeks (24 patients with cirrhosis Child-Turcotte-Pugh A and 25 patients with cirrhosis Child-Turcotte-Pugh B in patients with hepatic impairment, as these are the intented patient population). Doses up to bid were used.

The treatment with BI 685509 in patients with cirrhosis of different aetiologies, with hepatic impairment with Child-Turcotte-Pugh A and B was safe and well-tolerated. All AEs were of mild or moderate intensity. No treatment-related SAEs, as defined by the Investigator, occurred, or led to treatment discontinuation. Orthostatic intolerance occurred in the higher dose groups, and did not lead to treatment discontinuation, but recovered during continued treatment. Treatment with BI 685509 had no effect on laboratory parameters, including liver enzymes and bilirubin.

An effect of BI 685509 on the predicted placebo-corrected mean change from baseline QTcF ( $\Delta\Delta$ QTcF) was seen. In both patient groups, there was a dose dependent increase of  $\Delta\Delta$ QTcF up to 13.7 ms, with the upper 90% CI > 20 ms. In one patient group (Child-Turcotte-Pugh A) this was concomitant with a change of the predicted placebo-corrected mean change from baseline heart rate ( $\Delta\Delta$ HR) of > 10 beats per minute (bpm), but not in the other patient group [c34995868-01]. No such effect was seen in healthy Caucasian volunteers (Trial 1366-0003) for dosing regimens achieving exposure relevant for this trial. In healthy Asian volunteers (Trial 1366-0013), at a dose regimen achieving exposure relevant for this trial (i.e. starting dose of TID up to a final dose of TID), increase of  $\Delta\Delta$ QTcF was seen up to 11.7 ms with 90% CI < 20 ms, concomitant with an increase of  $\Delta\Delta$ HR of nearly 10 bpm.

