#### 1.4.2 Risks

Trial participants will be exposed to trial-related risks due to exposure to the investigational medicinal product (BI 685509), the trial procedures and other risks. For details refer to Tables 1.4.2: 1, 1.4.2: 2 and 1.4.2: 3 below.

Table 1.4.2: 1	Overview of trial related risks - investigational medicinal product (BI
	685509)

Possible / known risks of clinical relevance	Summary of data, rationale for the risk	Mitigation strategy
Potential AEs such as hypotension / orthostatic dysregulation, tachycardia, peripheral oedema and gastrointestinal events such as diarrhoea, abdominal pain and nausea	Primarily related to the vasodilatory effects and subsequent reactions or gastrointestinal effects which are directly related to the mechanism of action	To minimise the risk of severe or serious side effects, participants of this trial will only be exposed to doses that have been safely administered to healthy volunteers and patients in the preceding trials (refer to the IB [ $c02778238$ ] and Sections 1.2.1 and 4.1.2 ). All trial participants will be monitored for AEs, and BP and HR will be measured daily (by the trial participant at home) during the treatment period. Trial participants
		with oedema or gastrointestinal side effects will be managed by standard of care, and trial participants with a known history of orthostatic dysregulation and those with a SBP <100 mmHg or a DBP <70 mmHg will be excluded. In addition, up-titration to the maintenance dose within each treatment group will occur at weekly intervals in order to increase the tolerability of the trial medication with regards to cardiovascular effects.
Potential QT-interval prolongation	Refer to Section 1.2.3	Trial participants with long QT / QTcF- interval, trial participants with a family history of long QT syndrome, or those using concomitant therapies known to increase the risk of Torsade de Points will be excluded from the trial (refer to Sections 3.3.3 and 4.2.2.1 ). ECGs will be performed at each visit in the randomised treatment period of the trial, and trial medication will be discontinued in the event of a prolonged QT / QTcF-interval (refer to Section 3.3.4 ).

Table 1.4.2: 1 (cont.)Overview of trial related risks - investigational medicinal product (BI
685509)

Possible / known risks of clinical relevance	Summary of data, rationale for the risk	Mitigation strategy

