#### 3.3.4.1 Discontinuation of trial treatment

An individual trial participant will discontinue trial medication if:

- the trial participant wants to discontinue trial treatment. The trial participant will be asked to explain the reasons but has the right to refuse to answer.
- the trial participant develops an AE: •
  - CTCAE Grade 3 or higher and the AE was assessed by the Investigator as related to the trial treatment; OR
  - CTCAE grade 4 or higher regardless of attribution to the trial treatment 0
- the trial participant has repeatedly shown to be non-compliant with important trial procedures and, in the opinion of both the investigator and sponsor representative, the safety of the trial participant cannot be guaranteed as he / she is not willing or able to adhere to the trial requirements in the future.
- the trial participant needs to take concomitant medication that interferes with the safety/efficacy of the investigational medicinal product or other trial treatment (refer to Section 4.2.2.1). If short-term, acute use of a restricted concomitant therapy is required (e.g. 5-7 days of antibiotic treatment for an infection), this will not automatically require discontinuation of BI 685509. Similarly, if a trial participant needs to modify a dose, where only a stable dose is permitted (e.g. NSBBs / carvedilol, statins, anti-viral therapy for HBV), this also will not automatically require discontinuation. In both cases, the Sponsor should be consulted.
- the trial participant meets the criteria for hepatic injury (refer to Section 5.2.6.1.4 and • Appendix 10.2)
- the trial participant has an acute liver decompensation event such as VH, therapyrefractory ascites, overt encephalopathy, or other decompensation event based on Investigator judgement
- trial participants with worsening of their liver function (e.g. increase of Child Turcotte • Pugh score of more than 2 points with clinical evidence of deteriorating liver function in the opinion of the Investigator). Refer to Child-Turcotte-Pugh classification method in Appendix 10.3
- trial participants with a QT or QTcF interval > 500 ms, or an increase of QT or QTcF • of > 60 ms from the pre-dose value at Visit 2 / randomization (baseline). Such cases must be reported as AEs
- the trial participant can no longer receive trial medication for other medical reasons such as surgery, AEs, other diseases

- the trial participant's treatment assignment has been unblended due to an emergency situation

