#### 5.2.4 Electrocardiogram

The 12-lead ECGs will be recorded at the time points specified in the Flow Chart; the ECGs should be performed prior to blood sampling and intake of trial medication

During the dose-titration period (i.e. when up-titration is occurring) and at the subsequent visit, 12-lead ECGs will also be performed approximately 1 hour and 2 hours after intake of trial medication. These ECGs should precede the 1 hour and 2 hour (refer to Section 5.3.1).

ECGs must be administered by a qualified physician, nurse or technologist. The Investigator or delegate will evaluate whether the ECG is normal or abnormal and assess clinical relevance. An ECG may be repeated for quality reasons and the repeated recording used for analysis. If necessary, additional ECGs may be recorded for safety reasons.

Dated and signed print-outs of the ECG, with findings, should be documented in the trial participant's medical record. Clinically relevant abnormal findings will be reported either as a baseline condition (if identified at the screening visit [Visit 1a]) or otherwise as AEs and will be followed up and / or treated as medically appropriate. ECG abnormalities will be carefully assessed by the Investigator or delegate, and if trial discontinuation criteria are met (refer to Section 3.3.4.1), the trial participant will be discontinued from the trial.

Copies of ECGs will be sent to a central ECG Supplier for storage purposes. This will enable a subsequent centralised and independent re-evaluation if necessary.

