#### 7.2.6 Safety analyses

Adverse events will be coded using the Medical Dictionary for Drug Regulatory Activities (MedDRA). Standard BI summary tables and listings will be produced. All adverse events

with an onset between start of treatment and end of the REP, a period of 7 days after the last dose of trial medication, will be assigned to the on-treatment period for evaluation.

Safety analyses will be done by "treatment at onset" principle. All treated trial participants will be included in the safety analysis. In general, safety analyses will be descriptive in nature and will be based on BI standards. No hypothesis testing is planned.

Statistical analysis and reporting of adverse events will concentrate on treatment-emergent adverse events, i.e. all adverse events occurring between start of treatment and end of the REP. Adverse events that start before first drug intake and deteriorate under treatment will also be considered as 'treatment-emergent'.

Frequency, severity, and causal relationship of adverse events will be tabulated by system organ class and preferred term after coding according to the current version of the Medical Dictionary for Drug Regulatory Activities (MedDRA) at database lock.

Laboratory data will be analysed both quantitatively as well as qualitatively. The latter will be done via comparison of laboratory data to their reference ranges. Values outside the reference range as well as values defined as clinically relevant will be summarised. Treatment groups will be compared descriptively with regard to distribution parameters as well as with regard to frequency and percentage of trial participants with abnormal values or clinically relevant abnormal values.

Vital signs, physical examinations, or other safety-relevant data observed at screening, baseline, during the course of the trial and at the end-of-trial evaluation will be assessed with regard to possible changes compared to findings before start of treatment.

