7.8.4 ECG

Abnormal findings in 12-lead ECG will be reported as baseline conditions (at screening) or as AEs (during the trial) if judged clinically relevant by the investigator and will be analysed as such.

No separate listing or analysis of ECG data will be prepared.

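### The SAP plans no listing or summary of ECG data, so a QTcF shift, or a smaller change not judged clinically relevant, would not appear in its outputs

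*SAP*

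**What the plan says.** SAP 7.8.4 sends abnormal 12-lead ECG findings to baseline conditions (at screening) or to adverse events (during the trial) when the investigator considers them clinically relevant. It then closes with "No separate listing or analysis of ECG data will be prepared". The user-defined AE categories in SAP Table 7.8.1.5: 1 include none for QT.

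The protocol bears on this in several places:

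- **Risk.** Table 1.4.2: 1 in section 1.4.2 has a row for "Potential QT-interval prolongation".
- **Earlier data.** Section 1.2.3 reports, for trial 1366-0020 in hepatic impairment, a dose-dependent rise in the predicted placebo-corrected mean QTcF change "up to 13.7 ms, with the upper 90% CI > 20 ms".
- **Collection.** The Flow Chart schedules a "Resting 12-lead ECG" at every visit except 1b. Under footnote 21, during titration and at the visit after it, "vital signs and 12-lead ECGs will also be repeated approximately 1 hour and 2 hours after intake of the trial medication".
- **Site assessment.** Section 5.2.4: "The Investigator or delegate will evaluate whether the ECG is normal or abnormal and assess clinical relevance". Copies go to a central supplier for storage, with re-evaluation only if needed.
- **Mandatory AEs.** Section 3.3.4.1 covers QT or QTcF above 500 ms, or a rise of more than 60 ms "from the pre-dose value at Visit 2 / randomization (baseline). Such cases must be reported as AEs".
- **Analysis.** Section 7.2.6 has a sentence that starts from vital signs and the physical examination and then widens: "or other safety-relevant data observed at screening, baseline, during the course of the trial and at the end-of-trial evaluation will be assessed". The comparison it intends is with the state before treatment. ECG is not named.

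**The concern.** AE tables count patients who cross a limit or whose finding someone judged relevant. They cannot display or estimate a shift in the mean, which is the form in which the earlier trial reported its QTcF signal. If the SAP is followed as written, a report with no QT adverse event could be read as showing no QT effect, although none of its outputs displays an ECG value.

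The treatment of ECG also stands out within the SAP. Vital signs taken at the same pre-dose, 1-hour and 2-hour points get descriptive statistics, changes and figures (7.8.3). Individual laboratory data are listed (7.8.2), portal vein diameter is listed (7.9.1), and HVPG is still listed although its analysis was dropped (section 4). Section 4 attributes to the early stop only the loss of the HVPG analyses and of intercurrent-event reporting; it does not mention ECG.

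**Working it through.** The plan gives no figure on this point to reproduce. The check traces where an ECG value can go, counts what is collected, and then gauges how well the AE route would reflect a mean shift.

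**1. Routes into the outputs.** An on-treatment QT or QTcF value is visible only if (a) the investigator judges the finding clinically relevant (Protocol 5.2.4; SAP 7.8.1 and 7.8.4), or (b) it exceeds 500 ms or rises by more than 60 ms (Protocol 3.3.4.1). Sub-threshold changes can still enter by route (a). What remains unseen is a group-level shift, or an individual sub-threshold change that nobody flags.

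**2. Scheduled ECGs per completer** (Flow Chart and footnote 21):

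| Visit | ECGs | After first dose |
|---|---|---|
| 1a | 1 | 0 |
| 2 | 3 | 2 |
| 3, 4, 5 | 3 × 3 = 9 | 9 |
| 6, EoT, EoS | 3 | 3 |
| Total | 16 | 14 |

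This is the planned maximum. SAP section 4 says no participant finished 8 weeks.

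**3. How often a shift of the earlier size would trigger the +60 ms rule.** Suppose individual changes are normal with mean 13.7 ms. The documents give no SD, so 15, 20 and 25 ms are assumptions.

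p = P(Z > (60 − 13.7)/SD) = P(Z > 46.3/SD)

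| Assumed SD (ms) | p at a single ECG | Expected in 20 patients (20p) | P(at least one of 20) = 1 − (1 − p)^20 |
|---|---|---|---|
| 15 | 0.0010 | 0.02 | 2% |
| 20 | 0.0103 | 0.21 | 19% |
| 25 | 0.0320 | 0.64 | 48% |

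This is context only. The 13.7 ms is the largest predicted placebo-corrected mean, while 60 ms is an individual uncorrected trigger, and repeated ECGs would raise the chance of crossing it. The point is that most patients would stay below the rule, and that counts would not estimate the shift.

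**4. How precise a by-arm mean would be.** The 90% confidence half-width for a difference between arms of n patients each is t(0.95; 2n − 2) × SD × √(2/n).

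| n per arm | SD 10 | SD 15 | SD 20 | SD 25 |
|---|---|---|---|---|
| 20 (planned) | 5.3 | 8.0 | 10.7 | 13.3 |
| 10 (assumed) | 7.8 | 11.6 | 15.5 | 19.4 |
| 5 (assumed) | 11.8 | 17.6 | 23.5 | 29.4 |

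Half-widths are in ms. The number treated is not stated. With few patients, an interval of this width could neither establish nor exclude a shift of 13.7 ms. A patient listing needs no minimum sample size.

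**The case against.** The strongest reply is that the SAP does what the visible protocol describes. Section 5.2.4 sets up a qualitative site assessment, and no visible passage names a QTcF analysis. Section 7.2.6 does not mention ECG, and reporting new relevant findings against baseline conditions is a fair reading of it. The mitigation in the risk table is exclusion, monitoring and discontinuation, and that is in place. Vital signs have a reason for fuller treatment, since hypotension and syncope underlie secondary endpoints. The DMC has its own analysis plan, which is not available here. The earlier signal is mixed: a heart-rate rise accompanied it in one patient group, healthy Caucasian volunteers showed no such effect, and no hERG effect is known. The trial was stopped early, so a between-arm mean would say little. Numeric QT values may not be in the eCRF.

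Much of this stands. There is no breach of a named analysis, and the by-arm summary cannot be the core of the request. It does not remove the gap. DMC outputs are not shown to replace trial reporting, and the mixed earlier signal is a reason to list QTcF alongside ECG heart rate. Small numbers weaken a comparison of means but not a listing. Sites must already obtain QT and QTcF to apply section 3.3.4.1. Data entry is a real possible cost, limited by the early stop.

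**Conclusion.** The concern holds, as an inexpensive improvement that should be made. It is a stated decision not to show data on a named drug risk, not an error that invalidates any planned result. None of the scheduled ECG values (up to 16 per completer, 14 after first dose) would be listed or summarised under this SAP. At the size of the earlier signal, the mandatory +60 ms rule would be expected to pick up 0.02 to 0.6 of 20 patients at a single ECG, assuming normal changes with an SD of 15 to 25 ms. The conclusion rests on the text of SAP 7.8.4, not on those assumed SDs. It is confined to this SAP's outputs and says nothing about what the DMC saw.

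**What to change.** Replace the last sentence of SAP 7.8.4 with text such as:

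> All recorded QT, QTcF and ECG heart rate values, with change from the Visit 2 pre-dose value, will be listed by patient, visit and time point (pre-dose at visits with a dose, about 1 h and 2 h post-dose at Visits 2 to 5, and the single ECG at other visits). Patients with QTcF >450 ms (men) or >470 ms (women), QT or QTcF >500 ms, or a QT or QTcF increase >60 ms at any ECG after the first dose will be counted by treatment. If numbers allow, QTcF, heart rate and their changes will be summarised descriptively by treatment.

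The limits are the protocol's own. The 450 and 470 ms values come from the screening exclusion in section 3.3.3 and serve here only as reporting categories.

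If the by-arm summary is produced, add an ECG row to SAP Table 6.7: 1 and state its window. The early-discontinuation visit may fall up to 7 days after stopping, so a 1-day window like that for vital signs would class later ECGs from that visit as post-treatment. A cross-reference in 7.8.4 to the mandatory AE rule in Protocol 3.3.4.1 would help readers but changes no output.

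**Cost:** one listing, one count table and one optional summary; no new ECGs. If numeric values are not in the eCRF, they must be entered from site records. Any between-arm estimate will be too imprecise to rule an effect in or out, and the report should say so.

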7.9 OTHER ANALYSIS

7.9.1 Ultrasound

A listing for portal vein diameter will be provided.

7.9.2 Biomarker analyses

For all the biomarkers defined in Section 5.4.7, descriptive statistics will be presented.

In detail, for each marker the observed value will be analysed for the BMS via mean, standard deviation, median, Q1, Q3, normalized IQR (0.7413*IQR), minimum, maximum and gMean.

Other exploratory biomarkers may be reported in a separate biomarker report.

c43185880-01

Proprietary confidential information © 2024 Boehringer Ingelheim International GmbH or one or more of its affiliated companies.

7.9.3 PK analyses

Noncompartmental PK parameters will be calculated based on actual sampling times using a validated PK software (Phoenix® WinNonlin® 8.1).

Individual plasma concentration data and the PK parameters calculated thereof will be tabulated and graphically displayed. A patient's PK data will be flagged and excluded from the PK analyses in case of protocol deviations relevant to the evaluation of PK or in case of PK non-evaluability (refer to CTP Section 5.3.1).

